Patient Participants: Inclusion criteria are: 1) age ≥ 18 years, 2) score on the Generalized Anxiety Disorder [GAD-7] scale equal to or greater than 8, and 3) ability to speak English. Exclusion criteria are: 1) other psychological conditions rendering the person unlikely to benefit from a brief treatment, including psychosis, bipolar disorder, cognitive impairment, and active substance abuse or dependence (comorbid depression permitted); 2) current suicidal ideation or intent; 3) past suicide attempt or psychiatric hospitalization; 4) concurrent receipt of regular individual psychotherapy; 5) use of anxiolytic medication (including benzodiazepine and tranquilizers; antidepressants okay).

Maximum number of subjects

Enter the total maximum number of subjects to be recruited and enrolled 30-32

*required

Provide the enrollment breakdown number for each participant population

For example: n = 5 teachers, n = 30 students

Coaches: 5-7; Patient participants: up to 25

*required

What are the selection criteria for research participants?

Include sample size calculations, if applicable.

This exploratory pilot study will rely on convenience sampling. Coach participants (n = 5-7, to allow for attrition) will be recruited from the UNLV department of psychology and related departments. Patient participants (up to n = 25) will be recruited from the UNLV PRACTICE, UNLV campus, and the general community (see below).

This is a single-arm trial focused on feasibility and acceptability as well as preliminary clinical response (e.g., improvement in anxiety symptoms, engagement of purported psychological mechanism of avoidance) for a future R-series application to NIMH. There is no power analysis for such exploratory work; the sample sizes are not powered to detect treatment effects or statistical significance. Rather, these sample size estimates are determined by prior literature to demonstrate proof-of-concept and identify preliminary feasibility, acceptability, and appropriateness alongside initial demonstration of clinical impact.

See inclusion/exclusion criteria above for further details.

*required

Vulnerable Populations

Please check the population(s) that will be enrolled. Check all that apply.

Pregnant Women/Fetuses/Neonates

Minors with Parental Permission

	Minors who can consent themselves
	Prisoners
	Other
✓	None of the Above
*required	
Are yo	u excluding your populations based on gender, race or ethnic origins?
	Yes
✓	No
*required	

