- Anxiety Sensitivity Index (ASI-3), an 18- item self-report scale containing items specifying different concerns someone could have regarding their anxiety.
- Overall Anxiety Severity and Impairment Scale (OASIS), a 5-item self-report scale quantifying anxiety-related distress and impairment
- Multidimensional Experiential Avoidance Questionnaire (MEAQ), a 62-item self report assessment of avoidance. To be used to measure activation of target mechanism of avoidance.
- Cognitive Avoidance Questionnaire (CAQ); a 25-item self-report measure of the tendency to employ cognitive avoidance strategies when dealing with threatening intrusive thoughts. To be used to measure activation of target mechanism of avoidance.
- World Health Organization's Disability Assessment Schedule 2.0 (WHODAS 2.0); this 12-item generic health-status measure assesses functioning across six domains: communication, mobility, self-care, interpersonal, life activities, and participation. Item scores (0 = no difficulty to 4 = extreme difficulty or cannot do) are summed, with higher scores representing greater disability.
- Insomnia Severity Index (ISI); 7-item self-report questionnaire to assess cooccurring sleep difficulties (prevalent in anxiety)

2. First STARS Session:

After completing the Baseline Assessment, the patient ppt will meet with their study "coach" for approximately 45 min for the first session of the STARS program. Patient participants will complete a brief self-report inventories of anxiety (7-item Generalized Anxiety Disorder [GAD-7]) and co-occurring depressive symptoms (9-item Patient Health Questionnaire [PHQ-9]) at the beginning of every STARS session. These assessments are used in routine mental health care and primary care settings. These will be reviewed in session by the coach to monitor treatment response, identify session needs, and reinforce patient attempts at change. These scores will also be used by the PI to monitor treatment response and adverse events across participants.

The patient ppt will also complete the Credibility/Expectancy Questionnaire (CEQ) and the Working Alliance Inventory-short form (WAI-SF) at the end of Session 1, after treatment rationale has been explained. These will be paper forms that will be entered into the study database by the RA.

Both the baseline assessment and STARS session will be audio recorded for training and fidelity review.

3. Subsequent STARS sessions:

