Strategies for Treating Anxiety Research Study

Contact PI: [name], University of Nevada, Las Vegas

Statistical Analysis Plan

This single-arm study will examine the preliminary feasibility, acceptability, and clinical outcomes among coach and patient participants. Statistical analyses will be conducted with IBM SPSS version 28. Means and standard deviations (SDs) for primary implementation outcome measures will be calculated as summary statistics for: Acceptability of Intervention Measure (AIM); Feasibility of Intervention Measure (FIM); and Implementation Appropriateness Measure (IAM). Feasibility and acceptability outcomes also include examination and summary of the following: (1) recruitment and retention of patient participants (number completing all study treatment visits as a proportion of those enrolled); (2) external rating of coach fidelity to intervention (proportion of those rated as "satisfactory" or above on fidelity rubric); (3) and summary statistics of patient-rated working alliance (Working Alliance Inventory-short form).

Differences between pre- and post-treatment scores on clinical outcomes will be examined using paired t-tests. Effect sizes will be assessed using Hedge's g, with 0.2, 0.5, and 0.8 representing small, medium and large effect sizes, respectively. Clinically meaningful changes in the primary outcome will be evaluated with: the Reliable Change Index (Jacobson & Truax, 1992), movement out of the clinical range, and the percent reduction in symptoms. RCI scores reflect the change in scores from baseline to posttreatment, divided by the standard error; therefore, it is a method of roughly estimating how far from zero the change in scores is per participant. RCI scores indicative of clinically significant improvement were greater than or equal to 1.96, or a decrease in score of roughly two standard errors (Jacobson & Truax, 1991).

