Primary clinical outcomes include pre- and post-treatment changes anxiety severity (Hamilton Anxiety Rating Scale; HAM-A) and avoidance (Multidimensional Experiential Avoidance Questionnaire; MEAQ). Sustained change in anxiety symptoms on the HAM-A and MEAQ (pre-treatment and follow-up at 12 weeks) will also be examined with paired sample t-tests. Secondary clinical outcome is change between pre- and post-treatment global health status and functioning (World Health Organization's Disability Assessment Schedule 2.0; WHODAS 2.0) as assessed by paired sample t-tests. Additional exploratory analyses will examine pre- to post-treatment change and RCI scores in depressive symptoms (Patient Health Questionnaire; PHQ-9), given the high level of comorbidity between anxiety and depressive symptoms.

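### The SAP calls RCI ≥ 1.96 alone clinically significant improvement, with no clinical-range cut and no joint rule, so patients still in the clinical range can be counted

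*SAP*

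**What the plan says.** The second paragraph of the SAP introduces the patient-level criteria: "Clinically meaningful changes in the primary outcome will be evaluated with" three things, namely the RCI, "movement out of the clinical range, and the percent reduction in symptoms". It defines the RCI as the baseline-to-post-treatment change divided by a standard error, and says of it that "it is a method of roughly estimating how far from zero the change in scores is per participant". The next sentence sets the threshold and names it: "RCI scores indicative of clinically significant improvement were greater than or equal to 1.96, or a decrease in score of roughly two standard errors". No condition on the post-treatment score is attached.

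The third paragraph of the SAP names two primary clinical outcomes: "Primary clinical outcomes include pre- and post-treatment changes anxiety severity (Hamilton Anxiety Rating Scale; HAM-A) and avoidance (Multidimensional Experiential Avoidance Questionnaire; MEAQ". For PHQ-9 it plans, as exploratory work, "change and RCI scores in depressive symptoms (Patient Health Questionnaire; PHQ-9", and does not mention range movement.

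The protocol describes HAM-A and MEAQ under the baseline assessment without a clinical cut for either. Of MEAQ it says "To be used to measure activation of target mechanism of avoidance". The only numerical threshold for clinically significant anxiety in either document is an entry criterion on another scale: "score on the Generalized Anxiety Disorder [GAD-7] scale equal to or greater than 8".

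**The concern.** The label goes beyond what the SAP itself says the index measures. An RCI of 1.96 or more shows that a score has moved by more than measurement error would readily explain. It does not show that the patient has reached a non-clinical level. A very anxious patient can improve reliably and still be clearly anxious, and the stated wording counts that patient as clinically significantly improved.

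The criterion that could correct this, leaving the clinical range, cannot be applied as written because no cut is given. It could be chosen after the data are seen. Even with a cut, separate counts of reliable change and range movement would not show how many patients meet both.

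The reported proportion is at stake. The protocol presents the pilot as a source of preliminary clinical response for a later grant application and a powered randomized trial. Readers may carry forward a figure labelled clinically significant improvement when it means only change beyond error.

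**Working it through.** **The plan's own figure.** The 1.96 threshold is the two-sided 5% point of the standard normal distribution (1.95996). The SAP states no alpha for the RCI; this reading is inferred because it reproduces the number. The threshold concerns change only.

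**What the rule leaves out.** Let B be the baseline score, P the post-treatment score, r the reliability of the scale, and c the clinical cut.

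- SAP label: (B − P) / SE ≥ 1.96. P enters only through the difference.
- Joint rule: (B − P) / SE ≥ 1.96 **and** P below c, among patients with B above c.

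The two rules differ for every patient who starts above c, changes reliably, and ends above c.

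**How large the difference could be.** The documents give no SD, reliability, pre–post correlation or cut, so all the model inputs below are assumptions; only the sample sizes come from the protocol (minimum 15, up to 25).

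Model, in SD units with the cut at 0: B ~ N(k, 1), P ~ N(k − d, 1), correlation ρ, and SE of the difference = √(2(1 − r)).

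Mid case: k = 1, d = 0.8, r = 0.80, ρ = 0.5.

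- SE of the difference = √(2 × 0.20) = 0.632, so reliable improvement needs a fall of 1.96 × 0.632 = 1.24 SD.
- In range at baseline: Φ(1) = 0.841.
- RCI ≥ 1.96, given in range at baseline: 0.376.
- RCI ≥ 1.96 and below the cut after treatment, given in range at baseline: 0.238.
- Share of those labelled who are still in range: (0.376 − 0.238) / 0.376 = 0.367.

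The last three results come from numerical integration of the bivariate normal. A check with 2,000,000 simulated patients gives 0.375, 0.238 and 0.367.

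| Enrolled | In range at baseline | RCI ≥ 1.96 alone | Joint rule | Difference |
|---|---|---|---|---|
| 15 | 15 × 0.841 = 12.6 | 12.6 × 0.376 = 4.7 | 12.6 × 0.238 = 3.0 | 1.7 |
| 25 | 25 × 0.841 = 21.0 | 21.0 × 0.376 = 7.9 | 21.0 × 0.238 = 5.0 | 2.9 |

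**Sensitivity of the still-in-range share.**

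- k from 0.5 to 1.5, d from 0.5 to 1.2, r from 0.7 to 0.9, ρ = 0.5: from 0.106 (k = 0.5, d = 1.2, r = 0.7) to 0.709 (k = 1.5, d = 0.5, r = 0.9).
- Letting ρ also run from 0.3 to 0.8: from 0.078 to 0.758.
- Moving only the baseline mean of the mid case to 1.5 SD above the cut: 35% labelled by RCI alone, 15% by the joint rule, and a still-in-range share of about 57%.

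**The case against.** The strongest reply is that the end state is already in the plan. Range movement is one of three listed criteria, so a patient who changes reliably but stays in range would appear there as not having moved out. No success threshold or go/no-go decision depends on the RCI, and a reader of the SAP can see exactly what was counted. On this view only a loose label remains. The joint rule is one convention, to which the documents do not commit. The PHQ-9 sentence does not itself repeat the label. The illustration rests wholly on assumed inputs and spans a very wide range.

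Much of this is fair, and it limits the severity. The range criterion is present as a concept, the illustration is not evidence about this trial, and carrying the label over to PHQ-9 is an inference. The objection does not remove the point. The range criterion has no cut on any of the scales concerned, separate counts do not give the number meeting both, and for PHQ-9 no range count is planned beside the RCI. The mismatch between what the SAP says the index measures and what it calls the result is internal to the SAP and needs no outside convention.

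Three further matters are secondary and add no weight: the criteria refer to a single primary outcome although two are named; a clinical range may not exist for MEAQ, given its role as a mechanism measure; and because entry is on GAD-7, some patients may start outside a HAM-A range, with no statement of how they are counted.

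**Conclusion.** The concern holds, as a minor one. As written, the SAP can count patients who remain in the clinical range as clinically significantly improved. That follows from the wording and needs no assumption. Its size is unknown. Under the assumed mid case about 37% of those labelled are still in range, a difference of roughly 2 patients of 15 or 3 of 25; the assumed ranges give about 8% to 76%. The consequence is limited because the counts are descriptive, the protocol says the exploratory single-arm sample is not powered for treatment effects, and the mean-change analyses do not depend on the label.

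**What to change.** In the SAP:

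1. For HAM-A, MEAQ and PHQ-9, call RCI ≥ 1.96 *reliable improvement*. Define it as baseline minus post-treatment, divided by the standard error of the difference, so that the sign and the denominator are explicit.
2. Reserve *clinically significant improvement* for reliable improvement plus crossing a cut on the same scale, fixed before analysis, among patients in the clinical range at baseline. Report how many start outside that range.
3. Where no cut can be justified, possibly for MEAQ, say so and report reliable change only.
4. State whether the primary outcome for these criteria is HAM-A, MEAQ or both.
5. Optionally, report reliable deterioration (RCI ≤ −1.96).

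The cost is SAP wording and the choice of a justified cut for each scale where one exists. The proportion called clinically significantly improved may fall and its denominator may shrink. No new data are needed, and the paired t-tests and Hedges' g stay the same.

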Background on the STARS program. The PI developed the intervention to be delivered by coach participant to patient participants (see UNLV IRB study UNLV-2022-145 for iterative development and stakeholder involvement of this protocol). It is rooted in foundational principles from cognitive behavioral therapy (CBT) and streamlined in such a way that is intended to be delivered by nonspecialists. The STARS (strategies to treat anxiety research study) program consists of eight 30-min sessions (although the first session may last 45-to-60-min) conducted individually between a coach and patient participant. The first session focuses on (a) psychoeducation, (b) explaining the CBT model of anxiety, (c) selecting specific treatment targets from either worry management (for generalized anxiety symptoms; notably, uncontrollable worry) and exposure (for panic, phobia, or other anxiety related to avoidance), and (d) creating an exposure action plan ("homework; planned anxiety treatment activities for the week). Subsequent sessions focus on success or difficulties with the homework/activity plan for the week, including measurement-based care using repeated assessment of anxiety and depression symptoms to track treatment response.

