No portion of the screening assessment administration will be recorded. Any endorsement of an exclusion criteria will cease participation in the screener as soon as the assessment measure is complete (e.g., once the entire MDQ is completed, not just a single item on the MDQ). Ineligible participants will be informed of the following: "We have completed our screening questions and I appreciate your time. I'm sorry, but our criteria for you to continue in the study have not been met." They will be offered a list of community resources for mental health services (see attached).

All identifying information collected as part of the eligibility screener will be stored in an electronic database on a secure server and will be password protected. Eligibility screening data will be labeled with a unique study identification number. The link between the personal identifiers and the related eligibility screening data will be kept until the end of the study. Deidentified information will be kept indefinitely.

Patient Participants: Baseline and Subsequent Assessments; STARS Program

1. Baseline assessment:

Participants who are eligible upon screening will be asked to schedule a baseline assessment and first STARS session. This will be in-person at UNLV TREATment lab space on main campus. Informed consent for the intervention study will occur at this visit.

First, the patient participant will meet with a research assistant for approximately 1 hour - 1.25 hours. They will be sent the informed consent document ahead of time to review. During the meting, the RA will first describe the study, answer any questions, and obtain informed consent. At that point, patient participants will be considered "enrolled." They will then complete a clinical interview (HAM-A) administered by the RA, provide demographic information, and complete six additional self-report study measures (ASI-3, OASIS, MEAQ, CAQ, WHODAS, ISI):

- Hamilton Anxiety Rating Scale (HAM-A), an interviewer-rated measure consisting of 14 items, each defined by a series of symptoms, to measure both psychic anxiety (mental agitation and psychological distress) and somatic anxiety (physical complaints related to anxiety). A corresponding interview guide will be used to increase the reliability. This measure has demonstrated sensitivity to change in clinical trials.

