The patient ppt will meet with their assigned Coach for 8 weekly sessions. Sessions 2-8 are expected to last 30 min. These sessions will be audio recorded and uploaded to the study database alongside the patient ppt's responses to GAD-7 and PHQ-9 for ongoing supervision and monitoring by [name].

4. Subsequent assessments

See the Assessment Schedule for details of follow-up assessments.

Patient Participants: Patient participants will complete post-intervention assessments at Week 8, including brief exit interview questions of their experiences. They will also complete follow-up assessments to assess maintenance of treatment effects at 6 and 12 weeks after completion of treatment. These assessments can be conducted by Zoom, in-person at UNLV, or over the telephone. Patient participants will receive \$40 incentive payment for completion of each assessment (baseline, post-treatment, 6- and 12-week follow-up) for a total possible incentive of \$160.

Assessments and STARS sessions will be audio recorded for training and fidelity review.

BL, Wk 8, FU 1, FU2:

For all study-related assessment timepoints once enrolled, an RA will conduct the HAM-A clinical interview. The remaining instruments will be completed as self-report forms either using paper forms, for RA entry into the study database, or entered directly into the study database as survey responses by the participant.

For BL and Wk 8 assessments, this assessment visit will occur in person in the TREATment Lab space prior to their scheduled STARS coaching visit. After completion of the HAM-A interview, the participant will have time to complete the remaining self-report inventories.

For follow-up assessments (FU 1 and FU 2), the HAM-A will be conducted over the telephone and/or Zoom. The self-report forms will be completed either over the telephone (by verbal self-report from the patient participant) or possibly by emailing a survey link via REDCap. (Note: UNLV REDCap is still pending as of 7/11/2023 per [name], ORI Data Privacy Officer, so exact functions have not yet been trialed to see if we can build this function into our database.)

STARS Visits:

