At each STARS visit, the participant will complete a GAD-7 (anxiety screen) and PHQ-9 (depression screen) at the start of session. This will be a paper self-report form that is then used in session for review between the coach and patient participant as is often the case in routine clinical care. This data will be entered by the coach into the STARS visit note at the end of the visit.

All assessments will be labeled only with the Study ID number, visit number (e.g., BL for baseline), and date of visit. The electronic study database will be the ultimate record for data capture; any responses on paper forms will be immediately transferred to the study database (same day) by the RA or Coach and all or any paper forms will be shredded as soon as possible.

Risk of Harm Protocol (Patient Participants).

During screening, potential patient participants will be asked explicitly and specifically about suicidality to ensure appropriateness and eligibility for this study. It is possible that responses may "trigger" the risk of harm protocol, including any positive responses to CSSRS items 1 ("Have you wished you were dead or wished you could go to sleep and not wake up?") or 2 ("have you actually had any thoughts of killing yourself?"). The CSSRS administration will be followed, such that any positive response to Item 2 will result in additional questions being asked. At the end of the CSSRS, the rater makes a risk determination of low, moderate, or high. Instructions for low, moderate, and

high risk assessments are detailed in the attached Risk of Harm Protocol, which we use across lab studies. All assessors have immediate access to the PI ([name]) for questions or for [name] to contact the patient participant in any instances of moderate or high risk disclosure to conduct further assessment and take any necessary action (e.g., calling emergency services to conduct a wellness check).

Throughout the study, suicidal thoughts or behaviors may be identified such as on the PHQ-9 (item #9, "Thoughts that you would be better off dead, or thoughts of hurting yourself in some way?") or in conversation (e.g., self-report of a patient participant during STARS session). If a participant endorses a score of ≥ 1 on item #9 of the PHQ-9 or self-reports any suicidal ideation, the C-SSRS will be administered to determine risk and the Risk of Harm protocol will be followed.

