(a) Clinical deterioration and suicide risk: We will attend to clinical deterioration for both participant protection purposes, and in order to document the safety of the intervention. We define "clinical deterioration" as 1) the development of passive or active suicidal ideation (as confirmed by investigators) at any point during the study; 2) the development of manic or psychotic symptoms; or 3) ≥30% increase in PHQ-9 or GAD-7 scores at follow-up assessment. Rating scales may not adequately capture clinical deterioration in all patients. For this reason, we will encourage coaches to report when they notice a worsening of clinical state that is not identified by the above criteria.

Any patient participant exhibiting \geq 30% increase in GAD-7 scores for two consecutive sessions will trigger specific case-focused individual supervision with [name], which may include specific guidance on following sessions, outside recommendations, and/or direct contact of [name] with the patient.

Despite excluding individuals with active suicidality at screening, a patient participant may later (at sessions 2-8) endorse item 9 on the PHQ (reporting having "Thoughts that you would be better off dead, or thoughts of hurting yourself in some way?"). This is unlikely to happen but is possible. This will be handled on a case-by-case basis and a positive answer endorsement to item 9 is not necessarily indicative of active suicidality (e.g., there may be thoughts of death but not actually wanting to die/kill oneself). Any patient participant who endorses PHQ-9 item 9 (suicidal ideation) will trigger the coach to conduct the C-SSRS (Columbia Suicide Severity Rating Scale). Any indication of moderate or high risk will trigger the PI to immediately telephone and evaluate the patient participant to determine presence of suicidal ideation and level of risk. Also, any client exhibiting \geq 30% increase in PHQ-9 scores for two consecutive sessions will trigger specific case-focused individual supervision with [name], which may include specific guidance on following sessions, outside recommendations, and/or direct contact of [name] with the patient.

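### PHQ-9 is collected at every session but analysed only as a pre-to-post change, so a patient without a post score leaves the analysis although earlier scores are stored

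*SAP*

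**What the plan says.** The SAP's only analysis of depression is in its final paragraph: "Additional exploratory analyses will examine pre- to post-treatment change and RCI scores in depressive symptoms (Patient Health Questionnaire; PHQ-9"). The test comes from its second paragraph: "Differences between pre- and post-treatment scores on clinical outcomes will be examined using paired t-tests". The SAP names no repeated-measures model, has no rule for missing scores, and does not say which PHQ-9 is the pre score and which the post score.

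The protocol collects much more. Under *STARS Visits*: "At each STARS visit, the participant will complete a GAD-7 (anxiety screen) and PHQ-9 (depression screen) at the start of session". Under *Subsequent STARS sessions*: "The patient ppt will meet with their assigned Coach for 8 weekly sessions". The background on the STARS program describes "measurement-based care using repeated assessment of anxiety and depression symptoms to track treatment response".

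At baseline, patients "complete six additional self-report study measures (ASI-3, OASIS, MEAQ, CAQ, WHODAS, ISI"). PHQ-9 is not in that list, so the pre score appears to be the one taken at the start of Session 1.

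**The concern.** A paired analysis needs both scores. A patient who attends some sessions and then stops may have several stored PHQ-9 scores but contribute nothing to the estimated change.

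The protocol gives a reason why such losses may not be random. Under its risk-minimisation procedures, item (a), patients who develop active suicidal ideation are taken out of the study. Its payment example is a withdrawal after the week 6 or 7 session, with the Week 8 assessment still to come. Suicidal thoughts are item 9 of the PHQ-9 itself. The analysis can therefore lose patients because their depression worsened, and the remaining pairs could show too favourable a change. The planned sample is a minimum of 15 and at most 25 patients, so a few such cases count.

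The weekly course, which the protocol presents as the way response is tracked, is also never summarised.

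**Working it through.** The documents give no precision figure for PHQ-9 to reproduce, and no variances, correlations or dropout rate. The values below are assumptions: intercept variance 16, residual SD σ from 2 to 3 points, between-patient SD τ of the true Session 1 to Session 8 change up to 5 points, and residuals independent unless stated. The covariance is treated as known.

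**1. Scores outside the planned analysis.** If pre is Session 1 and post is Session 8, 8 − 2 = 6 scores per completer are not analysed. This is an inference, because the SAP does not name the occasions.

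**2. Complete data, no shape imposed on time.** With a separate mean for each session, the variance of the Session 8 minus Session 1 contrast is (V₁₁ + V₈₈ − 2V₁₈)/n. That is also the variance of the mean paired difference, so the ratio is exactly 1.00.

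**3. Complete data, straight line assumed.** With times 0 to 7, Σ(t − 3.5)² = 42. The fitted change, 7 × slope, has residual variance (49/42)σ² = 1.167σ², against 2σ² for two scores. With a random slope the variance ratio is (τ² + 1.167σ²)/(τ² + 2σ²).
- τ = 0: 1.167/2 = 0.58.
- σ² = 6 (σ = 2.45), τ = 3: (9 + 7)/(9 + 12) = 16/21 = 0.76. At n = 25 the SE falls from √(21/25) = 0.92 to √(16/25) = 0.80.
- σ = 2, τ = 5: (25 + 4.67)/(25 + 8) = 0.90.
- Random intercept with AR(1) errors, τ = 0: 0.80 at autocorrelation 0.3, 0.92 at 0.5 and 0.985 at 0.7.

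This gain comes from the assumed line and nearly vanishes under strong serial correlation. The line can also mislead: if an assumed true change of −5 levels off early, 7 × slope gives −4.27 to −4.85.

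**4. 25% of post scores missing, no shape imposed.** Suppose stopping is spread evenly over last sessions 2 to 7. The completers' paired variance is (τ² + 2σ²)/(0.75n). For the model, add the information from each stopping group, I = Σ nₖEₖ′Vₖ⁻¹Eₖ, where Vₖ is the covariance of the first k scores and Eₖ selects them. The variance is then c′I⁻¹c, with c the last-minus-first contrast.
- σ² = 6, τ = 3, n = 25: paired SE √(21/18.75) = 1.06; model SE 1.00, about 6% lower. Assuming a line as well would give 0.87.
- σ = 2 to 3, τ = 2 to 5: variance ratio 0.85 to 0.90, so the SE is 5 to 8% lower.
- In the same example, a likelihood model using only Sessions 1 and 8 lowers the SE by about 1%. That part comes from the Session 1 scores of those who stop; the rest comes from the middle scores.

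**5. Size of a selection effect.** If a fraction p lack a post score, and the mean changes are C in completers and D in the others, the all-patient mean is (1 − p)C + pD. The completers' mean differs from it by p(C − D). At p = 0.25 that is a quarter of the gap between the groups; one patient in 25 gives 1/25 = 4% of it. The gap itself cannot be derived from the documents.

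**The case against.** **Some who stop sessions may still have a post score.** The compensation section lets patients who discontinue treatment continue with the paid assessments. The deterioration definition refers to an "increase in PHQ-9 or GAD-7 scores at follow-up assessment", which implies that PHQ-9 is also taken outside sessions. The assessment schedule is an attachment not in the text. A separate Week 8 PHQ-9 would change the count of six and shrink both the missing pairs and the gain in step 4. This stands.

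**The outcome is exploratory.** PHQ-9 is neither a primary nor a secondary clinical outcome, and the protocol says that the pilot is not powered for treatment effects. A two-point description may be thought adequate. This stands too, and limits how much the point matters.

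**The session scores are not wasted.** They are reviewed in session, and "These scores will also be used by the PI to monitor treatment response and adverse events across participants". The gap is in the SAP's analysis only.

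**A stronger reading is tempting:** that six scores are discarded, so depression change is less precise than the collected data allow. The documents do not support it as a general statement. Step 2 shows no loss with complete data, and the larger gains in step 3 depend on a straight line that nothing in the documents establishes.

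**Conclusion.** The point holds in limited form. The SAP has no analysis that keeps patients without a post PHQ-9, although the protocol stores their session scores. Withdrawal for active suicidal ideation is a stated route by which patients with worsening depression could be lost, so the change could look too favourable. The direction is plausible, but the size is unknown.

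The precision gain is small: none with complete data and no assumed shape, and about 5 to 8% of the SE with 25% of post scores missing under the variances assumed above. It is less if a Week 8 PHQ-9 is obtained from those who stop, and estimating the covariance from 15 to 25 patients will give some of it back. The main reasons to change are to keep every enrolled patient with session scores in the estimate and to describe the weekly course. For an exploratory outcome this is a worthwhile improvement, not a flaw that undermines the plan.

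**What to change.** In the SAP's final paragraph, replace the PHQ-9 pre-to-post analysis with wording such as:

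> PHQ-9 change from Session 1 to Session 8 will be estimated from all session scores of all enrolled patients with a likelihood-based repeated-measures model (SPSS MIXED), with session as a category. The covariance will be a random intercept and slope by patient or, if that does not converge, a random intercept with AR(1) errors. The estimated change will be reported with a 95% CI. A linear trend will be given only as a supplementary description. The two-point change and RCI will be reported descriptively, with the number of patients contributing.

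Name the pre and post occasions. If the assessment schedule includes a separate Week 8 PHQ-9, say how it relates to the Session 8 score, which is taken before that session is delivered.

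The cost is a few sentences and one procedure in software the SAP already names; no new data are needed. The downsides are a covariance choice, slightly more analysis work and a missing-at-random assumption. For patients withdrawn as they worsen, that assumption is easier to defend when their last recorded session scores are in the model, but it can still fail if the worsening came after those scores. With complete data the estimated change should agree closely with the paired difference, so little is lost.
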